### **9.1 General Considerations**

Descriptive statistics will be provided for selected demographic, safety, PK, and efficacy data. Descriptive statistics of continuous data will include the number of subjects, mean, median,

---

standard deviation, minimum & maximum. Descriptive summaries of categorical data will use frequency counts and percentages. Graphical summaries of the data may be also presented.

## **9.2 Subject Accountability**

The number and percent of subjects in each analysis set (Full Analysis Set, Safety Analysis Set, and PK Analysis Set), who complete or discontinue treatment (including reasons for discontinuing), and who complete or discontinue from the study (including reasons for discontinuing) will be summarized using the Full Analysis Set.

## **9.3 Important Protocol Deviations**

Protocol deviations will be recorded during the conduct of the study and those identified as important will be listed by subject using the Full Analysis Set.

## **9.4 Demographic and Baseline Characteristics**

### **9.4.1 Subject Demographics**

Descriptive summaries of subject demographics and baseline characteristics will be produced using the Safety Analysis Set. Demographic data will include:

- Race: American Indian or Alaska Native, Asian, Black or African American, Native Hawaiian or Other Pacific Islander, White, and Other. If one subject has more than once race is reported, the subject will be categorized as More than One Race Reported.
- Ethnicity: Not Hispanic or Latino, Hispanic or Latino, Not Reported, Unknown, and Other.
- Gender: Male and Female
- Age at Screening in years
- Baseline weight
- Baseline height
- Baseline BMI

Additionally, demographic and baseline characteristic data for CF patient cohorts will include:

- Region (US vs Other)
- FEV1 (L)
- Percent predicted FEV1 (ppFEV1) (%)
- ppFEV1 categories ( $\leq 40\%$ ,  $> 40\% - \leq 70\%$ ,  $> 70\% - \leq 90\%$ ,  $> 90\%$ )
- FVC (L)
- Percent predicted FVC (ppFVC) (%)
- FEV1/FVC

- Sweat chloride
- CFQ-R Respiratory Symptoms domain
- CFTR mutation status
- Use of CFTR modulators at baseline (Y vs N)
- Use of inhaled hypertonic saline at baseline (Y vs N)
- Use of inhaled bronchodilator at baseline (Y vs N)
- Use of chronic inhaled antibiotic at baseline (Y vs N)
- Use of dornase alfa at baseline (Y vs N)
- Use of inhaled corticosteroids at baseline (Y vs N)
- Use of azithromycin at baseline (Y vs N)
- Sputum pseudomonas status at baseline (Positive vs Negative)

All demographic data will be listed by subject.

#### **9.4.2 Eligibility**

Inclusion and exclusion eligibility criteria not met will be listed by subject for all screen failures.

#### **9.4.3 Medical History**

The Medical Dictionary for Regulatory Activities (MedDRA) version 23.0 or later will be used to code medical history events to a system organ class (SOC) and a preferred term (PT). Descriptive statistics summaries of subject incidence of medical history events will be provided by SOC and PT.

Medical history will be listed by subject.

### **9.5 Safety Analyses**

All safety summaries outlined in this section will be created using the Safety Analysis Set.

#### **9.5.1 Adverse Events**

AEs will be recorded from time of signed consent through to EOS. The PI and clinical facility staff are responsible for detection, recording and reporting of events that meet the criteria and definition of AEs. The investigator will determine the severity and relationship of an AE associated with use of the study drug, and will identify serious adverse events (SAEs). All AE data summaries will report these as recorded on the eCRF.

MedDRA version 23.0 or later will be used to code all events categorized as AEs to a SOC and PT.

An overall summary of AEs will be provided. The overall summary will include the number and percent of subjects experiencing an event as well as the number of events in each of the following

---

categories: AEs, TEAEs, treatment-related TEAEs, SAEs, TESAEs, treatment-related TESAEs, and AEs resulting in study drug withdrawal, study discontinuation, and death. Categories are not mutually exclusive.

Descriptive statistics summaries of subject incidence of AEs will be summarized for all TEAEs, treatment-related TEAEs, TESAEs, treatment-related TESAEs, and AEs resulting in study drug withdrawal or study discontinuation will be tabulated by SOC in alphabetical order and PT in descending order of frequency. Summaries will include count and percent of subjects as well as number of events.

Descriptive statistics summaries of subject incidence of TEAEs by SOC, PT, and relationship to study drug will be provided. Subjects will be counted once under the closest relationship reported within each SOC and PT. Events will be counted the number of times they occur within each SOC and PT.

Descriptive statistics summaries of subject incidence of TEAEs by SOC, PT, and severity will be provided. Subjects will be counted once under the highest severity reported within each SOC and PT. Events will be counted the number of times they occur within each SOC and PT.

All AEs will be listed by subject. Separate by-subject listings of SAEs and of AEs resulting in study drug withdrawal or study discontinuation will be provided.

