6.1. Primary Endpoint

1. The incidence and frequency of adverse events over time through end of study using escalating multiple doses in NHVs and in CF patients.

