5	NHVs	Double-blind	12 (8 active: 4 PBO)	≤ 180 mg Day 1, 2, 3
2b	CF Patients	Double-blind	Up to 6 (4 active: 2 PBO)	≤ 40 mg dosed on Day 1, 2, 3; ≤ 40 mg dosed on Day 22, 23, 24
3b	CF Patients	Double-blind	Up to 6 (4 active: 2 PBO)	≤ 65 mg dosed on Day 1, 2, 3; ≤ 65 mg dosed on Day 22, 23, 24
4b	CF Patients (ppFEV1 > 70%)	Double-blind	Up to 12 (9 active: 3 PBO)	≤ 180 mg dosed on Day 1, 2, 3; ≤ 180 mg dosed on Day 22, 23, 24
6	CF Patients	Double-blind	Up to 24 (18 active: 6 PBO)	≤ 490 mg dosed on Day 1; ≤ 490 mg dosed on Day 15; ≤ 490 mg dosed on Day 29

The dose escalation schedule is outlined in **Figure 1**.

Figure 1: Dose Escalation Schedule

* Cohorts 1-4 each use 2 sentinel subjects dosed before the rest of the cohort. Where specified, dose represents the highest dose that may be used in the cohort. The DSC or Sponsor may adjust the dose downward if indicated based on available safety data.

† specified dose given once on Day 1, Day 2 and Day 3

** Cohorts 2b, 3b, 4b, and 6 enroll in sequence per Figure 1 and after associated DSC approval.

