## 2. OBJECTIVES, ENDPOINTS AND HYPOTHESES

### 2.1 Objectives and Endpoints/Estimands

The objective of the study is to assess the safety, tolerability, pharmacokinetics (PK) of ARO-ENaC in normal healthy volunteers (NHVs) and patients with Cystic Fibrosis (CF).

Endpoints
Primary

The incidence and frequency of adverse events (AEs) over time through end of study using escalating multiple doses in NHVs and in CF patients.

Secondary

Changes from pre-dose baseline in serum electrolytes in NHVs and CF patients as a safety measure.

Changes from pre-dose baseline in Forced Expiratory Volume (FEV1) in NHVs as a measure of safety.

Pharmacokinetics of ARO-ENaC in NHVs and in CF patients.

Exploratory

Changes from pre-dose baseline in FEV1 in CF patients

Changes from pre-dose baseline in lung clearance index (LCI) in CF patients

Changes from pre-dose baseline in the revised cystic fibrosis questionnaire (CFQ-R) in CF patients

Rate of pulmonary exacerbations in CF patients receiving ARO-ENaC versus placebo (PBO)

Changes from pre-dose baseline in body mass index (BMI) in CF patients

- Plasma metabolite identification in NHVs (reported in a separate report outside of this study)
- Determination of urinary excretion and metabolite identification in NHVs (reported in a separate report outside of this study)
- Changes from pre-dose baseline to Day 18 in expression of  $\alpha$ ENaC using bronchoscopic brush biopsy samples in NHVs
- Changes from pre-dose baseline to Day 18 in expression of  $\alpha$ ENaC using bronchoalveolar lavage (BAL) samples in NHVs
- Changes from pre-dose baseline to Day 18 in cytokine levels as well as cell count and differential in BAL fluid in NHVs

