## 5. DEFINITIONS

### Study Day:

Day of study relative to the date of first dose of active drug or placebo. First dose date will be considered as Day 1. Calculated prior to first dose date as (date of measurement – date of first dose) and calculated after first dose date as (date of measurement – date of first dose + 1).

Baseline:

The last observation prior to the first dose of active drug or placebo. The baseline value may be an unscheduled or repeated measurement.

Change (absolute) from baseline:

The arithmetic difference between a post-baseline value and baseline for a given time point: change (absolute) from baseline = (post-dose value – baseline value).

Percent change from baseline:

The percent change between a post-baseline value and baseline for a given time point: [(post-dose value – baseline value) / baseline value] \*100%

Treatment-emergent AEs (TEAEs):

TEAE will be derived as any AEs occurring on or after the first dose.

Treatment-emergent SAEs (TESAEs):

TESAE will be derived as any serious AEs occurring on or after the first dose.

Concomitant Medications:

Concomitant medications will be derived as any medications with an end date on or after the first dose.

Use of medications at baseline:

For each of the following medications: CFTR modulators, inhaled hypertonic saline, inhaled bronchodilators, chronic inhaled antibiotics, inhaled corticosteroids, dornase alfa, and azithromycin, any use within 30 days prior to first dose will be considered as use at baseline. Dornase alfa and azithromycin will be identified by the Preferred Drug Name as coded by WHODrug. All other medications will be identified as recorded on the CF-Concomitant Medications eCRF.

Sputum pseudomonas status at baseline:

Any pseudomonas (as collected on the Airway Infection eCRF) present within 30 days prior to first dose will be considered as positive at baseline.

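### The primary endpoint is adverse events over time with multiple doses, but no planned AE summary shows by arm whether events change between cycles or doses in the CF cohorts

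*SAP*

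**What the plan says.** Protocol 6.1 gives the primary endpoint as "The incidence and frequency of adverse events over time through end of study using escalating multiple doses in NHVs and in CF patients". SAP 2.1 repeats it: "The incidence and frequency of adverse events (AEs) over time through end of study using escalating multiple doses in NHVs and in CF patients".

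The CF cohorts are dosed more than once, with gaps. The entry for Cohort 4b in Table 4 (Protocol 7.1) reads "≤ 180 mg dosed on Day 1, 2, 3; ≤ 180 mg dosed on Day 22, 23, 24". Cohorts 2b and 3b follow the same calendar, and Cohort 6 is dosed on Days 1, 15 and 29. All CF patients are followed to Day 113.

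On analysis, SAP 5 uses one open window: "TEAE will be derived as any AEs occurring on or after the first dose". SAP 9.5.1 states that "AEs will be recorded from time of signed consent through to EOS". It then plans four kinds of summary:
- an overall table of subjects and events by AE category;
- tables by system organ class and preferred term ("Summaries will include count and percent of subjects as well as number of events");
- tables by relationship to study drug;
- tables by severity.

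In the last two, a subject counts once per term at the closest relationship or highest severity, and "Events will be counted the number of times they occur within each SOC and PT". SAP 9 sets the columns as dose and regimen, with placebo pooled across cohorts. Study day is not a grouping variable in any AE table. SAP 10 declares no major change from the protocol's analyses.

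**The concern.** Healthy volunteers receive one cycle on three consecutive days, so re-dosing after an interval is first tested in the CF cohorts. Protocol 7.2 says those cohorts are there to understand multiple-dose safety, and that Cohort 6 is there to compare the safety of a compressed regimen. Whether tolerability worsens or improves at the second cycle, or at the second and third doses, is therefore a central question for the primary endpoint.

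A whole-study count does not depend on the order in which events occurred, so the planned AE tables cannot answer it. They also combine events near dosing with a long follow-up in which background CF events are expected. At the primary analysis they combine subjects with very different observation times.

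**Working it through.** **1. The plan's own AE figure.** Table 5 (Protocol 12.1, SAP 3.2) gives the chance of at least one TEAE in a cohort as 1 − (1 − p)^n.
- n = 4, p = 0.3: 1 − 0.7^4 = 0.760 (stated 0.76).
- n = 9, p = 0.2: 1 − 0.8^9 = 0.866 (stated 0.87).

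All 14 cells reproduce to two decimals. Table 5 is itself a whole-study quantity with no time element.

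**2. Order does not matter in a cumulative table.** Cumulative subject incidence is 1 − Π(1 − p_i), and expected events are n × Σp_i. The interval risks below are assumptions for illustration, with intervals independent and at most one event per subject per interval.

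| Cohort (active n) | Interval risks | Cumulative incidence | Expected subjects | Expected events | Expected subjects by interval |
|---|---|---|---|---|---|
| 4b (9) | 10%, 30% | 1 − 0.9×0.7 = 37.0% | 3.33 | 3.6 | 0.9, 2.7 |
| 4b (9) | 30%, 10% | 1 − 0.7×0.9 = 37.0% | 3.33 | 3.6 | 2.7, 0.9 |
| 6 (18) | 5%, 10%, 20% | 1 − 0.95×0.9×0.8 = 31.6% | 5.69 | 6.3 | 0.9, 1.8, 3.6 |
| 6 (18) | 20%, 10%, 5% | 1 − 0.8×0.9×0.95 = 31.6% | 5.69 | 6.3 | 3.6, 1.8, 0.9 |

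Within each cohort only the last column differs, and no planned table contains it.

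**3. The data cuts do not separate doses.** The cuts are an optional interim at Day 37 for 2b-4b (SAP 7.2), the primary analysis at Cohort 6 Day 43 (SAP 7.3), and the final analysis (SAP 7.4). The last scheduled doses are Day 24 and Day 29, so every cut falls after the last dose of its cohort.

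**4. Observation time at the primary analysis.** Planned CF placebo is 2 + 2 + 3 = 7 subjects in 2b-4b, complete to Day 113, and 6 in Cohort 6. If Cohort 6 is cut at exactly Day 43:
- pooled placebo: (7×113 + 6×43)/13 = 1049/13 = 80.7 days on average;
- Cohort 6 actives: 43 days each;
- ratio: 80.7/43 = 1.88.

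The SAP does not say whether data after Day 43 are truncated. If they are kept and Cohort 6 averages d days, pooled placebo averages (791 + 6d)/13. At d = 78, the midpoint of 43 and 113, that is 96.8 days and a ratio of 1.24. At d = 113 the ratio is 1.

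**5. How much follow-up lies late.**
- After the Day 37 read-out: 113 − 37 = 76 days (67% of 113).
- After the Day 43 read-out: 113 − 43 = 70 days (62%).
- Protocol 5.8 reports that the sheep effect returned to baseline by 4 weeks after dosing. If that applied to humans (an assumption), effect could last to Day 24 + 28 = 52 in 2b-4b and Day 29 + 28 = 57 in Cohort 6. The days beyond are 61/113 = 54% and 56/113 = 50%.

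**The case against.** The strongest reply is that the SAP carries out the protocol's plan. Protocol 12.3 also has no time split, and the endpoint wording can be read as accumulated through end of study. That reading is possible, so a charge that the SAP departs from the protocol's AE analysis would not stand. What stands is that an endpoint worded over time and by multiple doses has no summary over time. If cumulative incidence is all that is meant, the endpoint should say so.

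A reader might also infer that timing is lost or that re-dosing safety goes unexamined. The documents do not support that. All AEs are listed by subject, which is workable with 4, 4, 9 and 18 active CF subjects. Laboratory tests (including potassium plots), vital signs, ECG, chest X-ray, spirometry and exacerbations are summarised by visit or timepoint. Numbers dosed at each scheduled dosing are tabulated (SAP 9.5.8). These outputs narrow the gap, but none summarises TEAEs by arm and dosing interval.

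A second tempting reading is that everything after Day 37 or Day 43 is off-drug. Protocol 5.2.1 says activity outlasts plasma and tissue exposure, so that period should be called follow-up.

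Two further objections have force. Keeping all dosed subjects in the denominator is ordinary Safety Set practice. The table shells are in a companion document that is not available here, although SAP 1 describes it as giving formats for outputs described in the SAP, and none of those is split by time.

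**Conclusion.** The concern holds for the AE summaries in the CF cohorts. No planned summary shows by arm whether TEAEs change between cycles in 2b-4b or between doses in Cohort 6, and no data cut supplies that contrast. The size is qualitative: opposite risk patterns give the same row (37% in the Cohort 4b illustration), and those risks are assumed. The observation-time imbalance at the primary analysis is about 81 against 43 days, if planned numbers are met, 2b-4b placebo subjects complete, and Cohort 6 is cut at Day 43. It shrinks if later data are kept.

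The point does not extend to healthy volunteers, whose three doses fall on consecutive days. No test or decision rule is affected, because SAP 2.2 plans no formal hypothesis testing. The change is worth making because it lets the primary endpoint address re-dosing, but it is a descriptive addition.

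**What to change.** Add to SAP 9.5.1, for the CF cohorts only, a descriptive TEAE table by onset interval giving subjects, percent, events, subject-days and events per subject-time.

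- **Cohorts 2b-4b:** Day 1 to before the Day 22 dose; Day 22 dose to Day 37; after Day 37 (nominally 21, 16 and 76 days).
- **Cohort 6:** dose 1 to dose 2; dose 2 to dose 3; dose 3 to Day 43; after Day 43 (nominally 14, 14, 15 and 70 days).
- **Denominators:** for a dosing interval, subjects who received the dose that opens it; for follow-up, subjects still followed.
- **Placebo:** shown separately by regimen (7 subjects in 2b-4b, 6 in Cohort 6), because the intervals differ.
- **Labels:** call the last row follow-up, not off-drug.
- **Partial onset dates:** state how they are assigned to intervals, since SAP 8.2 imputes some to the first of the month or to Day 1.

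Subject-time is needed because the intervals are unequal. The table uses onset and dosing dates already collected and changes nothing in trial conduct. The cost is two small panels rather than one table, sparse cells and a split placebo column, so it should be read descriptively.

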### **9.5.2      Laboratory Test Results**

Laboratory assessments include clinical chemistry, coagulation, hematology, urinalysis, and urine electrolytes. Microscopic urinalysis will also be performed as needed, with results listed by subject but not otherwise summarized. Clinical laboratory values will be expressed using the International System of Units (SI).

Descriptive statistics summaries of quantitative laboratory tests will be provided by scheduled visit. Derived changes and percent changes from baseline to each scheduled postdose visit will be included. Additionally, descriptive statistics for the peak post-baseline values will be included for the chemistry lab tests: ALT, AST, ALP, and BILI, and descriptive statistics for the lowest post-baseline values and lowest overall values will be provided for the hematology lab tests: HGB and PLT. Laboratory test values above or below the limits of detection will be set to the upper or lower limit values, respectively, for inclusion in the descriptive statistics summaries; values will be reported without imputation in the listings.

Plots of mean (+/- SD) key laboratory test results over time will be provided by study day. The key laboratory tests to be included will be: alanine aminotransferase, aspartate aminotransferase, total bilirubin, creatine kinase, creatinine, potassium, and sodium. SD bars below 0 will be set to 0.

Scatter plots of peak post-baseline total bilirubin [divided by upper limit of normal (ULN)] vs peak post-baseline alanine aminotransferase [divided by ULN] will be provided to visually evaluate drug-induced serious hepatotoxicity.

---

Additionally, select laboratory tests from serum chemistry, coagulation, and hematology will be programmatically graded using the National Cancer Institute (NCI) Common Terminology Criteria for Adverse Events (CTCAE) version 5.0 grading criteria (Appendix A). Laboratory test values above or below the limits of detection will be set to the upper or lower limit values, respectively, for programmatic grading. Using the CTCAE grades, shift tables describing changes from baseline to the maximum post-baseline grade will be provided for clinical chemistry, coagulation, and hematology laboratory results. The number and percent of subjects will be reported in each shift category. Assessments which are missing a baseline value or which are not graded at baseline will be summarized as unknown.

All laboratory data will be listed by subject. A separate listing of abnormal and out-of-range laboratory values will also be provided. Both listings will include normal reference ranges and flags (low, high, abnormal).

#### **9.5.3 Vital Signs**

Vital signs will include systolic and diastolic blood pressure, temperature, heart rate, respiratory rate (breaths/min), and pulse oximetry. Vital sign reporting will also include weight and BMI for CF patient cohorts.

Descriptive statistics summaries of vital signs will be provided by scheduled visit. Derived changes from baseline will be included in the summary.

Plots of mean (+/- SD) pulse oximetry (%) over time will be provided by study day. SD bars above 100% or below 0% will be set to 100% and 0%, respectively.

All vital sign data will be listed by subject.

#### **9.5.4 Electrocardiograms**

Descriptive statistics summaries of ECG parameters (heart rate, QT interval, PR interval, QRS interval, RR interval, QTcF, QTcB, and clinical interpretation) will be provided by scheduled timepoint. Derived changes from baseline will be included for quantitative parameters. The ECG clinical interpretation will be summarized using counts and percentages of subjects in each category (Normal, Abnormal NCS, Abnormal CS, Not Done).

All ECG data will be listed by subject.

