Blood samples will be collected from each subject for metabolic analysis per the SOA. Samples will be frozen at -80°C for analysis outside of this study.

Urine collections will be performed after dosing per the SOA.

Data Analysis:

Healthy volunteers and CF patients will be analyzed separately.

For each healthy volunteers and CF population, subjects will be analyzed by cohorts. Placebo subjects from each cohort will be pooled. In addition, CF patients will also be analyzed in aggregate and separately based on CFTR mutation status and based on use or no use at baseline of a stable regimen (last 2 months) of CFTR modulators/correctors as well as use or no use at baseline of inhaled hypertonic saline.

Screening, Compliance, Tolerability and Safety Data:

In general, safety analyses will be performed based on Safety Analysis Set, which includes all enrolled subjects who receive at least one dose of study drug (placebo or active). Post-dose safety assessments will be compared with measurements recorded at baseline. Treatment-emergent AEs will be summarized using the Medical Dictionary for Regulatory Activities (MedDRA) under version 23.0 or later by System Organ Class (SOC) and Preferred Term (PT). The incidence and frequency of treatment-emergent AEs, SAEs, related AEs, related SAEs, and AEs leading to discontinuation, will be summarized by cohort per SOC, PT, and severity. All AEs, SAEs will also be presented in listings. The duration of AEs will be determined and included in listings, along with the action taken and outcome. The incidence of laboratory abnormalities will be assessed using descriptive summary statistics and shift tables. Vital sign measurements will be summarized at each scheduled time point using descriptive statistics. Abnormal physical examination findings will be summarized by time point and presented in subject listings. ECG parameters, changes from baseline, and qualitative assessments will be summarized. Pregnancy and FSH test results will be listed separately.

Pharmacokinetics:

Plasma concentrations of ARO-ENaC product constituents will be used to calculate the following PK parameters:

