10.7. Safety Assessments

The safety of ARO-ENaC will be evaluated by collection of the following measurements performed at time points as specified in the SOA as well as CS changes from baseline to scheduled time points:

- Monitoring of AEs/SAEs
- Physical examinations
- Vital signs
- ECG measurements
- Chest X-rays
- Measurement of serum and urine electrolytes

- Spirometry
- Clinical laboratory tests (hematology, chemistry, coagulation, urinalysis)
- Concomitant medications/therapy
- Reasons for treatment discontinuation due to toxicity

The AE/SAE reporting period for an enrolled participant will begin when the participant provides informed consent. Treatment-Emergent AEs/SAEs will be those defined as following dose administration. All AEs/SAEs that occur during the AE reporting period specified in the protocol must be reported to Arrowhead Pharmaceuticals, Inc. regardless of the relationship of the AE to study treatment. Any known untoward event that occurs beyond the AE reporting period that the PI considers an SAE and possibly related to study treatment will be reported to Arrowhead.

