12.3. Safety/Tolerability Data

In general, safety analyses will be performed based on Safety Analysis Set, which include all enrolled subjects who receive at least one dose of study drug (placebo or active). Results will be summarized by population (NHV and CF) and cohort. Placebo subjects from each cohort will be pooled by population.

Treatment-emergent AEs will be summarized by System Organ Class (SOC) and Preferred Term (PT), classified from verbatim terms, with MedDRA version 23.0 or later. The incidence and percentage of participants with at least 1 occurrence of a PT will be included, per the most severe grade using a 3-point scale (mild, moderate, severe). The number of events per Preferred Term will also be summarized. Causality (relationship to study treatment) will be summarized separately.

The incidence and frequency of treatment-emergent AEs, SAEs, related AEs, related SAEs and AEs leading to withdrawal, dose modification, or treatment discontinuation will be summarized by population and cohort by SOC and Preferred Terms. All AEs, SAEs will also be summarized in listings. The duration of AEs will be determined and included in listings, along with the action taken and outcome.

Laboratory parameters will be summarized at each scheduled time point using descriptive statistics. The incidence of laboratory abnormalities will be summarized. Results for variables that are not coded will be presented in the listings as “below, within, and above” the normal limits of the laboratory. Pregnancy test results will be listed.

Vital sign measurements will be summarized at each scheduled time point using descriptive statistics. Physical examination findings will be summarized by time point and presented in patient listings.

ECG parameters at each scheduled study visit, changes from baseline and qualitative assessments will be summarized.

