#### **9.5.6 Chest X-Ray Findings**

Descriptive statistics summaries of chest X-ray findings will be provided by scheduled visit using counts and percentages of subjects in each category (Normal, Abnormal NCS, Abnormal CS, Not Done).

All chest X-ray data will be listed by subject.

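### ECG interpretation and chest X-ray are tabulated by visit with no within-subject comparison to baseline, so offsetting changes cannot be seen in the planned tables

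*SAP*

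**What the plan says.** SAP 9.5.4 summarises ECGs by scheduled timepoint. For the numerical parameters, "Derived changes from baseline will be included for quantitative parameters". The clinical interpretation gets category counts and percentages only: "The ECG clinical interpretation will be summarized using counts and percentages of subjects in each category (Normal, Abnormal NCS, Abnormal CS, Not Done"). SAP 9.5.6 follows the same pattern: "chest X-ray findings will be provided by scheduled visit using counts and percentages of subjects in each category", with the same four categories and no baseline comparison of any kind. Both sections add subject listings; for films, "All chest X-ray data will be listed by subject".

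Three protocol statements bear on this:

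- The Data Analysis part of the synopsis makes a general commitment: "Post-dose safety assessments will be compared with measurements recorded at baseline".
- Section 10.7 lists the safety measurements, ECG and chest X-ray among them, and bases the evaluation on these "as well as CS changes from baseline to scheduled time points".
- Section 12.3 is specific to ECG: "ECG parameters at each scheduled study visit, changes from baseline and qualitative assessments will be summarized".

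SAP 9.5.2 plans shift tables from baseline to the worst post-baseline CTCAE grade for laboratory results. SAP section 10 reports no major departure from the protocol's analyses.

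**The concern.** Counts by visit describe the group at each visit. They do not say who changed. One subject moving from Normal to Abnormal NCS and another moving back leave every count where it was, so the table shows no change when one subject has worsened. This is a first-in-human inhaled product, and repeat films are scheduled as part of the lung-safety monitoring. The natural question is how many subjects with a normal baseline assessment later had an abnormal one, by treatment group. No planned table gives that number.

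A smaller gap sits in the same sentences. Not Done is listed among the categories that receive a percentage, and the SAP does not define the denominator.

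**Working it through.** The plan states no figure to reproduce here. The check compares the texts and then asks what the planned tables can and cannot determine.

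**Step 1: what is left uncounted.** Protocol 11.2 makes a clinically significant abnormal assessment an adverse event if it appears during the study, or if it was there at baseline and has become significantly worse. The synopsis adds that diagnostic abnormalities not reported as adverse events are not to be entered as clinically significant. The Abnormal CS column therefore largely repeats the adverse event tables. What the ECG and X-ray tables add is the split between Normal and Abnormal NCS, and that split is not compared with baseline within subject.

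**Step 2: what equal counts allow.** Let n be the subjects in a group, b the number abnormal at baseline and p the number abnormal post-dose, with everyone assessed at both visits. The number newly abnormal can be any integer from max(0, p − b) to min(p, n − b).

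Group sizes come from protocol Table 4: 18 active in Cohort 6, 9 active in Cohort 4b, 4 active in each of Cohorts 2b and 3b, and pooled CF placebo of 2 + 2 + 3 + 6 = 13. The documents give no rate of abnormal baseline films or ECGs, so I assume about 25%, 50% and 75%, taken to whole subjects, and set p = b so that the table shows no change.

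| Group | n | Abnormal at both visits (b = p) | Newly abnormal subjects that fit |
|---|---|---|---|
| Cohort 6 active | 18 | 4 / 9 / 14 | 0–4 / 0–9 / 0–4 |
| Cohort 4b active | 9 | 2 / 4 / 7 | 0–2 / 0–4 / 0–2 |
| Pooled CF placebo | 13 | 3 / 6 / 10 | 0–3 / 0–6 / 0–3 |
| Cohort 2b or 3b active | 4 | 1 / 2 / 3 | 0–1 / 0–2 / 0–1 |

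For Cohort 6 with b = p = 9, the lower limit is max(0, 9 − 9) = 0 and the upper limit is min(9, 18 − 9) = 9. The upper limits are extremes that need as many subjects to improve as worsen. A milder case makes the same point: 2 worsen, 2 improve, and 9 + 2 − 2 = 9.

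**Step 3: what a shift table would add.** It replaces each range with the actual number of baseline-normal subjects who became abnormal. For subjects already abnormal at baseline it adds only moves between Abnormal NCS and Abnormal CS. A new finding in someone who stays Abnormal NCS is invisible with or without it.

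**Step 4: Not Done.** With 6 of 18 abnormal and 4 not done, the percentage is 6/18 = 33.3% if the missing are counted and 6/14 = 42.9% if they are not. With 2 not done it is 33.3% against 6/16 = 37.5%. These counts are illustrative.

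**Step 5: a limit on worst-category shifts.** Footnote 1 of protocol Tables 1.3 and 1.4 calls for one pre-dose and one post-dose ECG on each dosing day. That is 6 × 2 = 12 dosing-day ECGs in Cohorts 2b to 4b and 3 × 2 = 6 in Cohort 6. More ECGs give more chances of an abnormal one. SAP section 9 pools placebo across cohorts, so pooled CF placebo mixes 2 + 2 + 3 = 7 subjects on the first schedule with 6 on the second.

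**The case against.** The strongest reply is that nothing in the protocol is breached. It names shift tables only for laboratory abnormalities and anti-drug antibodies. It asks that qualitative ECG assessments be summarised, which SAP 9.5.4 does, and its analysis text asks for no chest X-ray table at all, so 9.5.6 goes further than required. The synopsis sentence about baseline is general, and a table by visit that includes baseline allows a comparison at group level. The reference in section 10.7 is to clinically significant changes, which reach the adverse event tables. With 4 to 18 active subjects per CF cohort, the listings can be read subject by subject. The study is descriptive with no hypothesis testing, and neither assessment is a named endpoint. For ECG, changes from baseline in the intervals are already planned. All of this stands. What it leaves open is a count, by treatment group, of changes not judged clinically significant.

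A reader might infer more than the documents support:

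- *That new abnormalities are hidden in CF patients whose baseline films are already abnormal.* In those patients a shift table adds only the move from NCS to CS, which the adverse event rule should already catch. How often baseline films are abnormal is not stated either.
- *That counting Not Done dilutes the percentage abnormal.* The denominator is undefined, and table formats are in a companion document that is not available here. This is a missing detail, not a demonstrated bias.
- *That SAP section 10 is wrong to report no major changes.* The protocol names no table that the SAP drops.

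**Conclusion.** The point holds as a minor reporting gap. The planned tables for ECG interpretation and chest X-ray cannot show within-subject change, which falls short of the protocol's general commitment to compare post-dose safety with baseline. Moves that cancel each other are lost from the summaries, mainly Normal to Abnormal NCS. In the largest arm, unchanged counts fit anywhere from 0 to 9 newly abnormal subjects of 18 at an assumed 50% baseline rate, and 0 to 4 at the assumed lower and higher rates. These ranges show what the tables leave undetermined; they do not predict how many subjects will change. The conclusion about the tables does not depend on the assumed rates. The underlying data are fully listed, and the case is stronger for films than for ECGs.

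**What to change.** In SAP 9.5.4 and 9.5.6, add by treatment group:

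- a shift table of baseline category (Normal, Abnormal NCS, Abnormal CS) against the category at each scheduled visit;
- the same against the worst post-baseline category, including films triggered by an adverse event, which a table by scheduled visit leaves out;
- percentages among subjects with the assessment done, with Not Done shown as a count only.

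Before programming, settle which film is baseline in the CF cohorts. The chest X-ray footnotes to protocol Tables 1.3 and 1.4 give Day 1 without saying whether it precedes dosing, while SAP section 5 takes the last observation before first dose.

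The cost is small: a few more tables per population, in a layout close to the laboratory shift tables. Worst-category ECG shifts need a note that the number of ECGs differs between regimens while placebo is pooled; the tables by visit should carry the main comparison. Showing new findings within Abnormal NCS would need a separate item on the case report form recording new or worsened against baseline. That is a larger, optional change.
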